
Statistical Analysis
	
A separate, detailed statistical analysis plan (SAP) will be finalized prior to locking the database. All analyses of safety and efficacy for this study will be descriptive in nature and presented by group. Subject demographics and baseline characteristics will be summarized. Subject data listings will also be provided.
 
Summaries for quantitative variables will include the mean, median, quartiles, standard error, minimum, and maximum. For qualitative variables, the summaries will include the number and percentage of subjects for each outcome, and the 95% CI, when appropriate. Any statistical testing will be considered exploratory and descriptive. All computations will be performed using SAS® (Version 9.4 or higher). Safety and tolerability will be assessed in terms of AEs, SAEs, safety laboratory data, and NEWS2 Assessments.
 
Adverse event data will be descriptively evaluated. All AEs will be reported in data listings. The incidence of post randomization adverse events, defined as AEs occurring after randomization will be tabulated by Medical Dictionary for Regulatory Activities (MedDRA) preferred term and system organ class, and by severity and relationship to study treatment. All laboratory results, NEWS2 Criteria, and other clinical measures will be summarized using appropriate descriptive statistics.

PROTOCOL NUMBER: CCB-CRISIS-01  
PROTOCOL VERSION FINAL DATE: 10SEPT2020

Page 17 of 58

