	
external laboratory to meet entry criteria provided such results are accurately documented and can be confirmed).
 

• Confirm subject meets all inclusion and no exclusion criteria.

 
Treatment
 
The treatment period is up to 5 days: standard of care alone (SOC) or SOC + brequinar 100 mg daily x 5 days. Data points such as NEWS2 Assessments and safety labs are to be collected from the EHR, a separate visit by study staff is not to be performed. Give the first dose of brequinar as soon as possible after randomization. See below regarding hospital discharge prior to Day 15.
 
Days 1 – 7 (8 AM ± 8 hours):
 

• If Day 1 is different date from Screening, confirm subject continues to meet all inclusion and no exclusion criteria.

• Randomize subject and record the time and date of randomization.

• Review Progress Notes and medication records to collect any new or ongoing adverse events or new or changed concomitant medications since previous visit (may be omitted on Day 1 if Screening visit is conducted on same day as Study Day 1). Repeat daily through hospital discharge.

• Collect SOC hematology/chemistry results from EHR on Day 1 (pre-dose) (may be omitted for Day 1 if Screening visit conducted on same date as Study Day 1) then daily through Day 7 or until the clinician decides daily testing is no longer necessary. Ensure that Day 1 samples are obtained prior to first dose of study drug, if applicable.

• Days 1 (pre-dose), 3, 5, 7:

– Collect NEWS2 Assessments from EHR.

– Collect results for inflammatory markers from EHR for those analyzed locally; collect, process and ship samples for DHO/brequinar PK and cytokine panel to be analyzed at the central laboratory per the Laboratory Manual.

– Collect, process, and ship nasopharyngeal viral load samples.

– Record hospitalization status (hospitalized, hospitalized in ICU, discharged); subject must be hospitalized Day 1 to meet inclusion criteria, do not record again.

• Dispense study medication (Days 1 through 5 if in brequinar group). Keep the brequinar study drug administration interval to 24h as much as possible. Record date and time of study drug administration.

• Drug accountability Day 7 ± 2 days.

 
Final Visit Day 15 (8 AM ± 2 days)
 

• Review Progress Notes and medication records to collect information for any new adverse events or changes in ongoing adverse events or new or

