--	--

	
changed concomitant medications since Day 7 (collect from EHR if subject still hospitalized, otherwise by phone or other digital media).
 

• Collect SOC hematology/chemistry results from EHR if subject still hospitalized.

• Collect results for inflammatory markers from EHR for those analyzed locally; collect and process samples for DHO and cytokine panel to be analyzed at the central laboratory on.

• Collect and process nasopharyngeal viral load samples.

• Record hospitalization status (hospitalized, hospitalized in ICU, discharged).

• Collect NEWS2 Assessments from EHR.

• If the subject is being discharged prior to Day 15, follow procedures below.

 
Day 29 (8 AM ± 3 Days)
 

• Determine survival status from EHR if available or by telephone/digital media per institutional guidelines.

 
Hospital Discharge Before Day 15
 
Subjects discharged from the hospital prior to the Day 15 visit are to return to a research facility when feasible for the remaining study visits. All scheduled study assessments are to be completed at these visits when conducted at a research facility.
 
For subjects in the brequinar treatment group discharged from the hospital prior to Day 5, the subject is to take home the remaining doses of brequinar for daily self-administration. All subjects (brequinar and SOC) should have the scheduled assessments, e.g. lab samples and the nasopharyngeal swab, on the day of discharge and enter these results on the appropriate EDC page. Following discharge, subjects are to return to the research or out-patient lab collection facility for the remaining study visits, if feasible. Out-patient lab results are to be entered into the EDC and reviewed by a member of the study team. It is important that every effort be made to have subjects return at least on Days 7 and 15, if feasible. Subjects in the brequinar group are to record brequinar dosing on the medication diary provided by the study team. The study team will arrange for the subject to return any unused study medication to the research facility.
 
For all subjects, if discharge occurs on Days 10, 11, or 12, ensure a hematology/chemistry sample has been obtained on the day of discharge and record these results on the appropriate EDC page. Following discharge, the subject is to return to the research or out-patient lab collection facility for the Day 15 visit if feasible. Out-patient lab results are to be entered into the EDC and reviewed by a member of the study team.
 
If discharge occurs on Days 13, 14 or 15, complete the Day 15 Final Visit activities prior to discharge. No further visits are required unless follow up is needed for a

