--	--

	
study drug-related AE or an SAE; the Day 29 mortality assessment is still to take place.
 
If the subject is unable or not permitted to return for planned study visits, the visit activities will be conducted by contacting the subject (phone or other digital media) except for the lab draw. The hematology/chemistry sample will be obtained via outpatient laboratory, if feasible and the results entered into the EDC and reviewed by the study team.
 
Study completion or the reason for study discontinuation will be recorded in the source document and the eCRF. A subject is considered completed the study if they have assessments through Day 15, whether conducted in the hospital or contacted via phone or other digital media.

Safety/ Tolerability
	
Safety/Tolerability
 
Adverse events will be collected from the time of informed consent through Day 15. After Day 15, collect/record only Serious Adverse Events (SAEs) or those judged by the Investigator or designated person to be related to study drug, including but not limited to potential hematologic toxicities. Post-randomization adverse events will be those with an onset after the date and time of randomization.
 
Subjects who develop Grade 3 or 4 toxicities are to be re-evaluated every 2 days, as feasible, until the toxicity returns to Grade <math>\leq 2</math> severity.

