### **6.2 Secondary Endpoints**

- Rates of/changes to the below clinical status measures through Day 15.
  - Hospitalization status
  - Duration of hospitalization in days
  - NEWS2 Assessments Days 1, 3, 5, 7, and Day 15 for hospitalized subjects.
- Mortality through Day 29

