#### 8.4.2 Study-Level Stopping Criteria

Following assessment by the Data Safety Monitoring Board (DSMB, see [Section 10.9](#)), the study is to be stopped as shown below:

- If  $\geq 4$  subjects on the brequinar treatment arm develop the same Grade 3 or 4 adverse event or symptomatic laboratory abnormality
- If  $\geq 8$  subjects on the brequinar treatment arm develop any Grade 3 or 4 adverse event or symptomatic laboratory abnormality.

### 8.5 Hospital Discharge Prior to Study Day 15

Subjects discharged from the hospital prior to the Day 15 visit are to return to a research facility when feasible for the remaining study visits. All scheduled study assessments are to be completed at these visits when conducted at a research facility.

PROTOCOL NUMBER: CCB-CRISIS-01  
PROTOCOL VERSION FINAL DATE: 10SEPT2020

Page 30 of 58

For subjects in the brequinar treatment group discharged from the hospital prior to Day 5, the subject is to take home the remaining doses of brequinar for daily self-administration. All subjects (brequinar and SOC) should have the scheduled assessments, e.g. lab samples and the nasopharyngeal swab, on the day of discharge and enter these results on the appropriate EDC page. Following discharge, subjects are to return to the research or out-patient lab collection facility for the remaining study visits, if feasible. Out-patient lab results are to be entered into the EDC and reviewed by a member of the study team. It is important that every effort be made to have subjects return at least on Days 7 and 15, if feasible. Subjects in the brequinar group are to record brequinar dosing on the medication diary provided by the study team. The study team will arrange for the subject to return any unused study medication to the research facility.

For all subjects, if discharge occurs on Days 10, 11, or 12, ensure a hematology/chemistry sample has been obtained on the day of discharge and record these results on the appropriate EDC page. Following discharge, the subject is to return to the research or out-patient lab collection facility for the Day 15 visit, if feasible. Out-patient lab results are to be entered into the EDC and reviewed by a member of the study team.

If discharge occurs on Days 13, 14 or 15, complete the Day 15 Final Visit activities prior to discharge. No further visits are required unless follow up is needed for a study drug-related AE or an SAE; the Day 29 mortality assessment is still to take place.

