## 10 ADVERSE EVENT REPORTING

An adverse event is any untoward medical occurrence in a patient or clinical trial subject administered a medicinal product and which does not necessarily have a causal relationship with this treatment. An AE can therefore be any unfavorable and unintended sign (including an abnormal laboratory finding), symptom, or disease temporally associated with the use of the medicinal product, **whether or not considered related to the medicinal product.**

Events that occur prior to informed consent will be entered as medical history; AEs that occur after informed consent will be entered on the AE form.

Subjects will be questioned and observed for evidence of AEs, whether or not judged by the Investigator or designated person to be related to study drug. All AEs will be documented in the subject's medical record and CRF. For any pre-existing condition or abnormal laboratory finding that changes in severity after dosing, this change should be recorded as an AE. New abnormal laboratory findings that are clinically significant are considered AEs.

All adverse events will be collected from the time of informed consent through Day 15. After Day 15, collect/record only Serious Adverse Events (SAEs) or those judged by the Investigator or designated person to be related to study drug. AE details are to be documented including start and stop date and times, whether continuous or intermittent, severity, any intervention utilized to correct the event (e.g., medication, surgery, or other therapy), outcome and the relationship to the study drug.

AEs identified in the protocol as critical to the evaluation of safety must be reported to the Sponsor by the Investigator according to the reporting requirements within the time periods specified in the protocol.

AEs determined by the Investigator to be related to study drug must be followed until resolution or until they are considered stable or for at least 30 days after discontinuation of study drug.

Any serious adverse events (SAEs) experienced after 30 days post the last dose of study drug should only be reported to the sponsor if the investigator suspects a causal relationship to the study drug.

Abnormal laboratory values or test results occurring after study enrollment constitute AEs only if they induce clinical signs or symptoms, are considered clinically significant, or require therapy.

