## 15 APPENDICES

### 15.1 Appendix A: CCB-CRISIS-01 Schedule of Events

CCB-CRISIS-01 Schedule of Events	Screen	D1	D2 - D7 (± 8 hours)	Final Visit D15 (± 2 days)	F/U Phone Call 2 weeks/ Survival (± 3 days)
Procedures					
Informed Consent	X				
AE/Concomitant Medications (daily until discharge)	X	X	D1-7	X	
Medical history / History of current illness	X				
Demographics, collect Height and weight	X				
Check for Physical Exam abnormalities	X				
Pregnancy Test (urine or serum)	X				
Hematology/Chemistry	X	X (pre-dose)	D1-7	X	
Inflammatory Markers*		X (pre-dose)	D3, D5, D7	X	
DHO/brequinar PK Sample Collection & Processing		X (pre-dose)	D3, D5, D7	X (DHO only)	
Swab collection for nasopharyngeal viral load		X (pre-dose)	D3, D5, D7	X	
Clinical SARS-CoV-2 testing RT-PCR	X				
Hospital Status			D3, D5, D7	X	
NEWS2 Assessments		X	D3, D5, D7	X	
Dispense Study Medication if assigned to brequinar**		X	D2 – 5		
Drug Accountability			D7		
Survival Assessment Day 29					X

Collect information from available electronic health record (EHR), Progress Notes, and medication records; a special visit by research staff is not to be performed. Results for Hematology, Chemistry and available inflammatory markers analyzed locally are to be obtained from the EHR; do not draw another set of labs. Missed samples due to hospital staff too busy or for technical reasons unable to obtain samples will not be counted as protocol deviations. Record urinalysis results if urinalysis is clinically indicated and results are available in the EHR. Note that if the subject is discharged before Day 15, follow instructions provided in [Section 8.5](#).

Note that any visits other than Screening/Day 1 may be conducted via telephone or digital media. Missed samples/assessments when phone visits occur will not be counted as protocol deviations.

\*Inflammatory markers are to be collected from the EHR when available; otherwise process and ship samples to the central laboratory per the Laboratory Manual. DHO and brequinar samples will also be sent to the central laboratory.

\*\*If a subject in the brequinar group is discharged prior to Day 5 (has not completed taking brequinar all 5 days) the subject may be dispensed study medication to take at home on a daily basis. In this instance the subject is also to be provided with the study medication diary for drug accountability purposes.

PROTOCOL NUMBER: CCB-CRISIS-01  

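### The survival check for mortality through Day 29 may be made as early as Day 26 with no later confirmation, so a death on Days 27 to 29 after discharge can be missed; a smaller gap affects adverse events before Day 15.

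*Protocol*

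**What the plan says.** All references are to the protocol version of 10 September 2020.

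- **Mortality endpoint.** Section 6.2 lists "Mortality through Day 29" among the secondary endpoints.
- **How it is measured.** The Synopsis heads the contact "Day 29 (8 AM ± 3 Days") and gives one task: "Determine survival status from EHR if available or by telephone/digital media per institutional guidelines". Section 9.5 repeats the day and the window. Neither asks for a second check or for a date last known alive.
- **Appendix A.** The last column is headed "F/U Phone Call 2 weeks/ Survival (± 3 days"), while the row beneath it places the survival assessment on Day 29. That column has no adverse event entry.
- **Adverse event period.** Section 10 states: "All adverse events will be collected from the time of informed consent through Day 15". After that, serious and drug-related events are still recorded.
- **Final visit.** The Synopsis gives "Final Visit Day 15 (8 AM ± 2 days"). For discharge on Days 13, 14 or 15, Section 8.5 says to "complete the Day 15 Final Visit activities prior to discharge. No further visits are required unless follow up is needed" for a drug-related or serious event.
- **Compliance.** Under Section 9.6, an activity done inside its window is not a protocol deviation.

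**The concern.** A symmetric window suits a measurement taken at a point in time, such as a platelet count. It suits a cumulative event endpoint less well. Mortality through Day 29 is known only when vital status has been confirmed on or after Day 29, and a check made earlier leaves the remaining days unobserved. The error in the death count runs one way, because an early check can lose a death but cannot add one.

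The same reasoning applies, more weakly, to adverse events and hospitalization status through Day 15 when the final visit is held on Day 13 or 14 and the subject is already at home or goes home that day. Adverse event rates are part of the primary endpoint (Section 6.1). With about 8 subjects on standard of care and 16 on brequinar, a single event is visible in the results.

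This concerns what is collected. An analysis plan can decide how to treat a subject last seen alive on Day 26, but it cannot supply the vital status that nobody sought afterwards.

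**Working it through.** The protocol states no figure on this point to reproduce. The check is window arithmetic, followed by an illustration under assumed event rates.

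**Inputs.** Mortality horizon Day 29 (Section 6.2); survival window ± 3 days (Synopsis, Section 9.5); adverse event horizon Day 15 (Section 10); final-visit window ± 2 days (Synopsis, Section 9.5); about 8 and 16 subjects per arm (Section 7.1). Time runs from 8 AM on Day 1, so Day d at 8 AM is d − 1 days.

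**1. Survival window.** It opens on Day 29 − 3 = 26 and closes on Day 29 + 3 = 32. A Day 26 check leaves 3 days unobserved out of 29 − 1 = 28: 3/28 = 10.7%.

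**2. Final-visit window.** It opens on Day 15 − 2 = 13 and closes on Day 15 + 2 = 17. A Day 13 visit leaves 2 days out of 15 − 1 = 14: 2/14 = 14.3%. A Day 14 visit leaves 1/14 = 7.1%.

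**3. Other routes for a death on Days 27 to 29.** Serious events are reported up to 30 days after the last dose, which is Day 5 + 30 = 35 for a full course. Three things keep this from closing the gap:
- after the last contact the site must happen to hear of the event;
- Section 10 tells sites not to report death from disease progression as a serious event, and the separate form for such deaths helps only if the site learns of them;
- the 30-day limit runs from a last dose that the standard-of-care arm does not have.

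**4. Illustration for mortality.** The protocol gives no expected mortality, so Day 29 mortality m is assumed to be 5%, 10% or 20%, with constant hazard and every subject checked on Day 26. The chance that a subject dies between the check and Day 29 is (1 − m)^(25/28) − (1 − m).

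| Assumed m | Per subject | Expected unseen among 24 | Chance of at least one |
|---|---|---|---|
| 5% | 0.0052 | 0.13 | 12% |
| 10% | 0.0102 | 0.25 | 22% |
| 20% | 0.0194 | 0.47 | 37% |

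These are upper bounds: every check is placed on the earliest day and nothing is learned by another route. If a death did go unseen, it would lower the arm's mortality by 1/8 = 12.5 points or 1/16 = 6.25 points.

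**5. Illustration for adverse events.** Suppose 30%, 60% or 90% of subjects have a first adverse event by Day 15 (assumed, constant hazard) and every final visit is on Day 13. The chance of a first event after the visit is (1 − p)^(12/14) − (1 − p), which is 0.037, 0.056 and 0.039. Among 24 subjects that is 0.9, 1.3 and 0.9. It overstates the loss considerably, because it counts inpatients and also serious and drug-related events, which other provisions cover.

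**The case against.** The strongest reply is that the protocol does not intend follow-up to end early. Sections 3.9 and 8.3 keep subjects under observation to at least Day 15, discharged or not. Section 8.5 waives further visits, not the collection period. Serious and drug-related events remain collectable after Day 15, inpatients have adverse events reviewed daily until discharge, and a readmission would usually qualify as a serious event. Symmetric windows are common, and this is a descriptive phase 1a study without a formal sample size.

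Much of that stands, and it rules out several stronger readings that a reader might infer:

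- **That survival could be closed on Day 24.** This takes the two-week heading in Appendix A literally from a Day 13 visit and then subtracts three more days (13 + 14 − 3). The row label in the same table, the Synopsis and Section 9.5 all fix the assessment at Day 29, and 15 + 14 = 29 explains the heading. Day 26 is the supported figure.
- **That later deaths and events are missed.** They can be missed; the routes above will catch some of them.
- **That adverse event collection closes on Day 13.** It does not. What is absent is a scheduled enquiry, chiefly for non-serious, unrelated events after discharge.
- **That the Day 29 contact never covers anything but survival.** Section 10.8 has telephone visits ask about possible hematologic toxicity, and it lists a Day 29 contact for subjects discharged before Day 7. The Synopsis, however, allows survival to be settled from the health record without a call.
- **That events in the gap will be analysed as absent.** The protocol does not say so, and censoring rules may sit in the analysis plan.

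None of this answers the mortality point. No section requires vital status to be confirmed on or after Day 29.

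**Conclusion.** The point holds for mortality and, more narrowly, for Day 15. A site that follows the protocol exactly can make its only survival check on Day 26, leaving up to 3 of 28 days (10.7%) unobserved for a discharged subject. For subjects out of hospital whose final visit is on Day 13 or 14, the last one or two days of the adverse event and hospitalization-status period have no scheduled enquiry; the likely loss is non-serious, unrelated events.

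The window arithmetic is certain. The expected loss is small and rests on assumed event rates: at most about 0.13 to 0.47 unseen deaths among 24 if Day 29 mortality is 5% to 20% and every check is made on the first permitted day. This does not undermine the trial. It is a one-directional weakness in collecting a mortality endpoint, in a study whose primary objective is safety, and it can be removed almost without cost.

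**What to change.** 1. In the Synopsis, Section 9.5 and Appendix A, have survival determined on or after Day 29, from Day 29 to Day 32. The upper limit is unchanged.
2. Record the date of death or, for subjects not known to have died, the date last known alive. This also shows whether a health-record lookup truly reaches Day 29.
3. Change the two-week wording in the Appendix A column heading to Day 29, to agree with its row label.
4. Keep Day 15 ± 2 for laboratory samples and swabs. Making the whole visit one-sided would cut its window from five days to three and conflict with the safety-laboratory window in Section 10.8.
5. In Section 8.5, for any subject out of hospital whose final visit took place before Day 15, add a short telephone contact on Days 15 to 17 to confirm adverse events and hospitalization status through Day 15.

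The cost is a survival-contact window of four calendar days (29 to 32) instead of seven (26 to 32), and a few extra short calls. Treatment and sampling are untouched.
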